## 10.2 Analysis of Primary Endpoint

The primary endpoint is the responder status in each treatment sequence based on TIS assessments at Weeks 17, 21, and 25. Following the estimand described in Section 10.1, a responder is defined as a subject with a TIS  $\geq 20$  points at Week 25 and at least at 1 of the previous scheduled visits (Week 17 or Week 21) who completes 24 weeks of randomized IMP treatment without the use of oral rescue corticosteroid treatment.

Therefore, for subjects who do not withdraw from IMP or the study for reasons which are related to the Ukraine war before Week 25, non-responders will include subjects who meet any 1 of the following:

- TIS  $< 20$  points at Week 25
- TIS  $< 20$  points at both Weeks 17 and 21
- Withdraw from treatment or the study or receive oral rescue corticosteroid treatment before Week 25 (Note: for subjects with corticosteroid taper starting at Week 17, only an increase to doses greater than 125% of the Baseline corticosteroid dose following corticosteroid taper starting at Week 17 will be considered a “rescue” corticosteroid dose)

To ensure that the treatment effect is not confounded by the intercurrent event of premature withdrawal from IMP or the study due to the Ukraine war, the hypothetical strategy is applied for this intercurrent event to quantify the treatment effect in the absence of the Ukraine war [Meyer et al, 2020; Collins et al, 2020]. For subjects who withdraw from IMP or the study for reasons which are related to the Ukraine war before Week 25, scheduled TIS assessments after withdrawal are missing. These missing values can be considered missing at random (MAR) and multiple imputation will be used to derive the hypothetical post-intercurrent event TIS values and the corresponding response variables assuming that the subjects with missing TIS values continue in the same way as similar subjects in the study who did not withdraw prematurely. Multiple imputation is a simulation based approach where missing values are replaced by multiple Bayesian draws from the conditional distribution of missing data given the observed data and covariates, creating multiple completed data sets. The completed data sets can then be analyzed using standard methods. Note: If no TIS values are available for the subject for any post-randomization visit during Study Period 1, the subject will be excluded from the mITT analysis set (see Section 6).

Details of the multiple imputation process for TIS values, derivation of the responder status are provided below:

### **(1) Imputation step**

- The multiple imputation process will be done for subjects who withdraw from IMP or the study for reasons related to the Ukraine war before Week 25 including all subjects who complete Study Period 1 without receiving rescue medication. TIS values in subjects who withdraw from IMP for reasons related to the Ukraine war before Week 25 that are assessed more than 6 weeks after the last IMP administration will be set to missing. Replacement of missing TIS values after discontinuation of IMP or the study (ie, monotone missings) for subjects who withdraw from IMP or the study for reasons related to the Ukraine war before Week 25 will be done using multiple imputations based on monotone regression with the covariates treatment, country, and Baseline MMT-8 ( $\leq 142$  points vs.  $>142$  points) and TIS values from previous visits (50 imputations) by SAS® PROC MI. The seed of the pseudo random number generator to be used to generate the imputations for missing values will be 30071234.

Note: If intermittent values are missing for any of the data included in the multiple imputation analysis, the intermittent values will be imputed first using a Markov Chain Monte Carlo (MCMC) method 50 times to create 50 data sets with only monotone missings. The corresponding data sets will be used as input data sets for replacement of the post-dropout missing values using monotone regression, as the preceding step led already to 50 data sets, the number of imputations in this step is to be set to 1. If

including country in the imputation model is not possible due to the sparseness of the data the variables Region (1): Japan, non-Japan and Region (2): USA, non-USA will be included.

- In each of the data sets subjects' responses will be derived according to the definition provided above.
  - The same multiple imputation process will be done for subjects who completed Study Period 1 without the use of oral rescue corticosteroid treatment but have missing TIS values.
  - In order to get data sets including all mITT subjects with complete response information, data of the following subjects will be added to each of the 50 data sets
    - Subjects who withdraw from IMP or the study for reasons not related to the Ukraine war before Week 25 or
    - Subjects who receive rescue medication in Study Period 1
- According to the definition above these subjects are all non-responders.

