## 4 Study Design

### 4.1 Study Design

This is a phase 3, multicenter, randomized, placebo-controlled, double-blind study of IgPro20 (subcutaneous immunoglobulin G [SCIG]) treatment in adult subjects with DM with or without muscle weakness.

This study consists of Screening and 3 treatment periods:

[figure not shown]
- Screening Period: Up to 2 months during which screening assessments must be completed
- Study Period 1: 24 weeks of either IgPro20 or placebo administration
- Study Period 2: 28 weeks of IgPro20 administration
- Study Period 3: additional treatment with open-label IgPro20 for subjects who have shown treatment benefit at Week 53

After Screening, subjects will be randomly assigned (1:1) to 1 of 2 sequences of double-blind weekly IMP treatment (0.5 g/kg IgPro20 and placebo). Subjects assigned to **Sequence A** will receive 0.5 g/kg IgPro20 for 24 weeks (Study Period 1) followed by 0.5 g/kg IgPro20 for 28 weeks (Study Period 2). Subjects assigned to **Sequence B** will receive placebo for 24 weeks (Study Period 1) followed by 0.5 g/kg IgPro20 for 28 weeks (Study Period 2).

The study data will be unblinded for the primary data analysis (ie, end of Study Period 1 [EOP1] analysis) after all subjects have completed all assessments for Study Period 1 and the data has been cleaned for primary data analysis. Subjects and caregivers, as well as site personnel involved in the conduct of the study, will remain blinded to treatment allocation until all subjects have completed all assessments for Study Period 2.

At the Week 53 Visit, subjects may be eligible to continue to Study Period 3 if their TIS was  $\geq$  20 points at the Week 49 Visit. In Study Period 3 subjects will receive open-label IgPro20 0.5 g/kg subcutaneous (SC) infusions weekly until the end of the study (see CSP Section 3.7).

The primary objective of this study is to assess the efficacy of IgPro20 0.5 g/kg weekly subcutaneous doses in comparison to placebo in adult subjects with DM, as measured by responder status based on TIS assessments at Weeks 17, 21, and 25.

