## 4.5 Determination of the Sample Size

The study is designed as a superiority study. The sample size calculation is based on the hypothesis that IgPro20 will have a higher responder rate than placebo based on the TIS assessments at Weeks 17, 21, and 25.

A responder is defined as a subject with a TIS  $\geq 20$  points at Week 25 and at least on 1 of the previous scheduled visits (Week 17 or Week 21) who completes 24 weeks of IMP without the use of oral rescue corticosteroid treatment.

Two recent studies [[Aggarwal et al, 2018](#) and [Tjarnlund et al, 2018](#)] of subjects with DM or polymyositis (PM) reported the responder rates by the International Myositis Assessment and Clinical Studies Group (IMACS) definition of improvement. However, there are currently no data in the literature on the responder rates in the TIS for subjects with DM. For power simulation, it is assumed that 65% of subjects randomized to IgPro20 and 30% of subjects randomized to placebo have a TIS  $\geq 20$  points at Week 17. Further, it is assumed that for each subject, the response at Week 21 is conditional on the response at Week 17, and the response at Week 25 is conditional on the response at Week 21. Assumptions used are detailed in [Table 3](#).

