**Table 3: Assumptions for Power Analysis**

Treatment Sequence A	Probability of having a TIS $\geq 20$ points at Week 17	Probability of having a TIS $\geq 20$ points at Week 21	Probability of having a TIS $\geq 20$ points at Week 25
A	65%	90%, if TIS $\geq 20$ points at Week 17	90%, if TIS $\geq 20$ points at Week 21
		20%, if TIS $< 20$ points at Week 17, or withdraw, or receive oral rescue corticosteroid treatment before Week 17	20%, if TIS $< 20$ points at Week 21, or withdraw, or receive oral rescue corticosteroid treatment before Week 21
B	30%	90%, if TIS $\geq 20$ points at Week 17	90%, if TIS $\geq 20$ points at Week 21
		10%, if TIS $< 20$ points at Week 17, or withdraw, or receive oral rescue corticosteroid treatment before Week 17	10%, if TIS $< 20$ points at Week 21, or withdraw, or receive oral rescue corticosteroid treatment before Week 21

A Treatment sequence A = 0.5 g/kg IgPro20 for 24 weeks followed by 0.5 g/kg IgPro20 for 28 weeks; Treatment sequence B = placebo for 24 weeks followed by 0.5 g/kg IgPro20 for 28 weeks.

Simulation shows a total of 126 subjects (63 subjects per treatment sequence) will be required for a power of 90% in 1-sided Fisher's exact test at a significance level of 0.025. Fisher's exact test is used in the power simulation as a close approximation to the exact logistic regression model in the primary endpoint analysis.

For further details see [Appendix 14.1](#).

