### 10.1 Primary Estimand

The primary interest is to quantify the treatment effect of IgPro20

- where the potential confounding effect of oral rescue corticosteroid treatment is excluded
- where the potential confounding of subjects who withdraw from treatment or the study before Week 25 and cannot provide sufficient data to demonstrate a benefit of treatment is excluded, and
- in the absence of premature withdrawal from IMP or the study before Week 25 due to the Ukraine war [[EMA Biostatistics Working Party, 2022](#); [ICH E9 \(R1\), 2020](#)].

The primary estimand in line with the primary interest of the study is described as follows:

- Population: the target patient population defined by eligibility criteria and who received any amount of randomized IMP and have post baseline efficacy results in Study Period 1 (mITT). See Section 6 for details.
- Variable: responder status based on TIS assessments at Weeks 17, 21, and 25
- Intercurrent events:
  - withdrawal from randomized IMP or the study, which is not related to the Ukraine war, or receiving oral rescue corticosteroid treatment before Week 25 is considered treatment failure
  - withdrawal from randomized IMP or the study which is related to the Ukraine war will be addressed using the hypothetical strategy [Meyer et al, 2020; Collins et al, 2020].
- Population-level summary: responder rate by treatment sequence

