## **(3) Pooling /combining step dataset**

- The corresponding results across the data sets are combined for overall inference using SAS® PROC MIANALYZE according to Rubin's rule to give the 1-sided p-value for hypothesis testing, the odds ratio (IgPro20 : placebo), and the corresponding 2-sided 95% confidence interval (CI). The primary endpoint analysis will utilize the mITT analysis set. Statistical significance will be assessed using a 1-sided alpha level of 0.025. The responder rate and corresponding 2-sided 95% CI will be estimated by treatment sequence. The primary endpoint analysis will also be provided for the subgroup of Japanese subjects.

Note: if a subject is erroneously assigned to the wrong baseline randomization stratum (eg, actual baseline MMT-8  $\leq 142$  points, but randomized in the stratum MMT-8  $> 142$  points) the analysis

---

will be done according to the actual stratum and not according to the stratum used for randomization. This applies to all analyses.

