average daily dose of Week 24 is reduced by at least 25%, as treatment with IgPro20 starts in both treatment sequences on the first day of Week 25.

For subjects who do withdraw from IMP or the study for reasons which are related to the Ukraine war before Week 25, the resulting missing values can be considered missing at random (MAR) and multiple imputation will be used to derive the hypothetical post-intervent event reduction of oral concomitant corticosteroid dose in percent (%reduction). Replacement of trailing missing %reduction values for weeks 17 to Week 24 (ie, monotone missings) will be done if the subject received oral corticosteroid medication at baseline using multiple imputations based on monotone regression with the covariates treatment, country, and Baseline MMT-8 ( $\leq$  142 points vs.  $>142$  points), baseline oral corticosteroid dose and %reduction values from previous weeks starting at Week 17 (50 imputations) by SAS® PROC MI. Note: If the subject did not receive any oral corticosteroid medication at baseline %reduction will be set to 0. The multiple imputation process will correspond to the one for the primary endpoint described in Section 10.2. A subject is considered a responder regarding this endpoint, if he/she is able to reduce the oral concomitant corticosteroid dose by at least 25% at Week 24, ie if %reduction is  $\geq 25$ .

For each of the 50 data sets resulting from the multiple imputation process the analysis of the 4th key secondary endpoint will be based on an exact logistic regression model including fixed effects for treatment, region (Japan vs. non-Japan), and Baseline MMT-8 ( $\leq$  142 points vs.  $>142$  points). The corresponding results across the data sets are combined for overall inference using SAS® PROC MIANALYZE according to Rubin's rule.

The 4 key secondary endpoints will be analyzed with an overall 1-sided alpha level of 0.025. The hypotheses associated with the key secondary endpoints will be formally tested and therefore adjusted for multiplicity. The key secondary analyses will be performed based on the mITT and repeated for the PP.

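### War-related withdrawals are imputed as if they could no longer be rescued or withdraw for other reasons, so their response rate is too high against the stated estimand in each arm

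*SAP*

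**What the plan says.** SAP Section 10.1 lists two kinds of intercurrent event. Rescue corticosteroids, or withdrawal for a reason other than the war, before Week 25 is treatment failure. War-related withdrawal is handled by the hypothetical strategy, so that the effect is estimated "in the absence of premature withdrawal from IMP or the study before Week 25 due to the Ukraine war".

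SAP Section 10.2 then assumes that war withdrawals "continue in the same way as similar subjects in the study who did not withdraw prematurely". Its imputation step works on a data set of war withdrawals, "including all subjects who complete Study Period 1 without receiving rescue medication". It imputes TIS by regression on treatment, country, baseline MMT-8 stratum and earlier TIS, and derives response from the completed TIS values. Subjects who were rescued in Period 1, or who withdrew for other reasons, are appended to each of the 50 data sets only after imputation, all as non-responders. Protocol Section 10.4.2.3 describes the same procedure.

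For the fourth key secondary endpoint (oral corticosteroid reduction of at least 25%), SAP Section 10.4 states: "The multiple imputation process will correspond to the one for the primary endpoint described in Section 10.2". Its estimand in Section 10.3 likewise counts rescue and non-war withdrawal as no reduction.

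**The concern.** The hypothetical strategy removes the war and nothing else. Had there been no war, a subject who left at Week 9 could still have been rescued, or have stopped for an adverse event or lack of efficacy, before Week 25. For every other subject these events count as failure. The imputation has no step that draws them. TIS is imputed in data that exclude the subjects who had them, and completing 24 weeks rescue-free, which is part of the responder definition, is simply granted. An imputed subject is given the response probability of a rescue-free completer with similar earlier TIS, not that of a subject still at risk of failing.

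At stake is the agreement between estimand and estimator in the confirmatory analysis, and in one of the four key secondary tests behind it. For completers who merely lack a TIS value the same data set is appropriate, because they are known not to have failed.

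**Working it through.** **Plan's own figures.** SAP Section 4.5 states that "it is assumed that 65% of subjects randomized to IgPro20 and 30% of subjects randomized to placebo" reach TIS ≥ 20 at Week 17. Response then persists with probability 0.9 from visit to visit. It is gained after a non-response with probability 0.2 (IgPro20) or 0.1 (placebo). Composite response is therefore:

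- IgPro20: 0.65×0.9×0.9 + 0.65×0.1×0.2 + 0.35×0.2×0.9 = 0.6025
- Placebo: 0.30×0.9×0.9 + 0.30×0.1×0.1 + 0.70×0.1×0.9 = 0.309

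SAP Table 14 gives medians of 0.603 and 0.317. Exact enumeration of the one-sided Fisher test at 0.025 with 63 per arm gives power 0.9037, against the stated 0.905. SAP Appendix 14.1.1 already counts withdrawal and rescue as non-response in these rates, so the sample size is not in question.

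**Upper bound on the excess.** Let f be an arm's risk of rescue or non-war withdrawal over Period 1, and assume that leaving because of the war is unrelated to prognosis. All responders are rescue-free completers, so completers respond at p/(1−f). The estimand rate for a subject at risk from baseline is p. The excess per imputed subject is p/(1−f) − p = p·f/(1−f). If war withdrawals are a share w of each arm, the difference shifts by w × [pA·fA/(1−fA) − pB·fB/(1−fB)]. Neither f nor w is in the documents. The values below are assumptions, with w = 10%.

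| f IgPro20 / placebo | Excess per imputed subject, IgPro20 / placebo (points) | Shift in the 29.35-point difference |
|---|---|---|
| 5% / 5% | 3.2 / 1.6 | +0.15 |
| 10% / 10% | 6.7 / 3.4 | +0.33 |
| 20% / 20% | 15.1 / 7.7 | +0.73 |
| 20% / 10% | 15.1 / 3.4 | +1.16 |
| 30% / 10% | 25.8 / 3.4 | +2.24 |
| 10% / 20% | 6.7 / 7.7 | −0.10 |
| 10% / 30% | 6.7 / 13.2 | −0.65 |

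The odds ratio is 3.39 without the excess, 3.72 in the 30%/10% row and 3.28 in the 10%/30% row.

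**Break-even.** The shift is zero when the placebo failure odds, f/(1−f), are 0.6025/0.309 = 1.95 times those on IgPro20, for example about 18% against 10%. Below that ratio the shift favours IgPro20.

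**Scale.** The standard error of the difference is √[(0.6025×0.3975 + 0.309×0.691)/63] ≈ 8.5 points.

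**Risk already survived.** With f = 20% and half of that risk elapsed at departure, the estimand rate on IgPro20 is 0.6025/0.9 = 0.669. The imputed rate is 0.6025/0.8 = 0.753. The excess is 8 points rather than 15.

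**Conditioning on earlier TIS.** A large-sample simulation with an assumed TIS model followed the plan's regression on earlier TIS, fitted in rescue-free completers. Entries are imputed minus estimand response, in points, IgPro20 / placebo.

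| Failure mechanism | War withdrawal after Week 9 | After Week 17 |
|---|---|---|
| None (benchmark) | +1.3 / +1.5 | +0.6 / +1.2 |
| Withdrawal unrelated to TIS | +7.9 / +4.0 | +4.1 / +2.4 |
| Rescue at low TIS only | +2.3 / +2.8 | +0.8 / +0.8 |
| Both | +8.0 / +6.0 | +3.9 / +2.7 |

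The benchmark row comes from the normal imputation model, not from the missing failure risk. After Week 9, earlier TIS absorbs most of the excess from low-TIS rescue (about 1 point remains above the benchmark) but little of that from unrelated withdrawal.

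**The case against.** Several points on the other side have force.

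- **Late leavers.** A war withdrawal has already survived part of the risk. Anyone rescued before leaving is appended as a non-responder, and TIS assessed within 6 weeks of the last IMP dose is kept. So p·f/(1−f) is a ceiling. A reader might infer from the table that imputed subjects respond at 75% where the estimand gives 60%. The documents do not support that as an expected value.
- **Treatment effect.** A reader might also infer that the procedure inflates the treatment difference. That does not follow. The sign depends on which arm fails more, and the documents give no failure rates. Protocol Section 1.4 names disease flare in the placebo arm as a risk, so more failures on placebo are plausible.
- **Sensitivity analysis 4** in SAP Section 10.2.1 excludes war withdrawals. If leaving because of the war is unrelated to outcome, it approximates the composite rate without the war. It is a useful check, but it does not change the primary analysis. Sensitivity analysis 3 extends the same imputation to further withdrawals. None of the planned analyses gives imputed subjects a risk of failure.
- **Declared assumption.** Section 10.2 openly models war withdrawals on subjects who stayed. For non-war withdrawal that is at least an explicit scenario. It does not cover rescue, because under Protocol Sections 3.1 and 5.3.1 rescued subjects continue in the study. They fit the stated description but are left out of the imputation data.
- **Aim statement.** Section 10.1 says that the confounding effect of rescue is to be excluded. Its intercurrent-event list does so by making rescue a failure, not by assuming it away.

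**Conclusion.** The mismatch is real. The estimand removes only the war, while the imputation also removes later rescue and non-war withdrawal for the subjects it imputes. Their response rate is overstated in each arm, by at most p·f/(1−f) per imputed subject if war withdrawal is unrelated to prognosis. The excess is smaller for later departures and where earlier TIS predicts failure.

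The effect on the treatment difference is likely small. At w = 10% it ranges from −0.65 to +2.24 points over the assumed failure rates, against a standard error of about 8.5 points. On this formula and the plan's rates it favours IgPro20 unless placebo failure odds are about 1.95 times those on IgPro20. The fourth key secondary endpoint inherits the mechanism for war withdrawals on baseline oral corticosteroids. The documents give no figures from which to size it there.

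The numbers of war withdrawals, rescues and other withdrawals are not in the documents, so every f and w here is an assumption. The planned 126 subjects and 90% power are unaffected. The point deserves correction because the repair is cheap and concerns the confirmatory analysis, not because the conclusion is expected to change.

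**What to change.** For each war withdrawal who was unrescued at the last on-treatment visit, replace the TIS-only imputation by one of two options:

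1. Impute composite responder status by logistic imputation on treatment, region, MMT-8 stratum and TIS up to that visit. Fit the model in non-war mITT subjects who were still on IMP and rescue-free at that visit, with later rescue or non-war withdrawal coded as non-response.
2. First draw later rescue or non-war withdrawal from that same at-risk set, then impute TIS only in those not drawn as failed.

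The at-risk restriction matters. Fitting in all other mITT subjects would include people who had already failed by that visit and would overcorrect downward. Requiring only that donors are still on IMP would let in rescued subjects, who continue treatment.

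Keep the current TIS imputation for completers with missing TIS. Apply the same at-risk approach to the fourth key secondary endpoint for war withdrawals on baseline oral corticosteroids.

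The cost is a change to the SAP wording, one extra imputation step and slightly lower responder rates. SAP Section 3 requires such decisions before unblinding. If that point has passed, report the analysis as a labelled sensitivity analysis.
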